11.0 STATISTICAL CONSIDERATIONS

This is a study of concurrent temozolomide and high dose radiation using biologic based target volume definition in patients with newly diagnosed glioblastoma (GBM).

The overall goal of this study is to determine if the treatment regimen described in this protocol is sufficiently promising to advance to a definitive randomized trial. Treatment for patients treated under this protocol will differ from standard care in the following ways:

- 1) High b-value diffusion-weighted and perfusion MRI will be used in target volume definition
- 2) The radiation dose to the boost volume will be 75 Gy based on earlier data demonstrating the safety and potential efficacy of this approach.
- **11.1** Primary objective: To improve overall survival at 12 months compared with published historical controls.

The final test addressing this aim will occur when the last enrolled patient completes 12 months of follow-up. If patients drop out or are lost to follow-up prior to 12 months, we will utilize the Kaplan-Meier approach to estimate OS at 12 months. Otherwise we will use the simple binomial proportion of patients who are alive within 12 months of treatment. We will test the null hypothesis that the true 12 months OS is equal to 0.65, based on recently reported survival rates from RTOG 0525 and RTOG 0825. The alternative hypothesis will be that 12 months OS is greater than 0.65. The test will be one-sided at an alpha=0.10 level. We will additionally use the Kaplan-Meier approach to estimated OS over time for all patients and according to MGMT and IDH1 status.

For example, MGMT status is an established prognostic factor in this setting with hazard ratios of approximately 2 for an endpoint of overall survival. On average we would expect a similar proportion of methylated patients in this trial as was observed for RTOG 0525 and RTOG 0825 (30%). However, with a sample size of 40, it is possible that the proportion of methylated patients will differ from 30% by a non-negligible amount. To account for this in the statistical analysis, we will weight patients so that the

weighted proportion of methylated patients is equal to 30%. Specifically, if p* denotes the observed proportion of methylated patients in this trial, the new weights will be .3/p* for methylated patients and (1-.3)/(1-p*) for unmethylated patients.

Sample size considerations:

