We anticipate enrolling 40 patients eligible to undergo a boost of radiation (>1 cc combined high b-value DW-MRI and perfusion MRI abnormality) at our institution. A similar protocol will be opened at a second center and treat an additional 40 patients in an identical fashion. This approach was chosen over a single multi-institutional trial protocol for logistical and financial reasons. Nevertheless, we expect to jointly analyze the data from all 80 patients following trial completion. Center will be included as a stratification variable in the analyses. Allowing for 10% of these patients to be non-evaluable for the primary endpoint, 40 (80) enrolled patients will provide greater than 80% power to detect an improvement in 12 month OS from 65% (based on historical controls) to 82% (40 patients) or 78% (80 patients). These results are based on an exact 1-sided test at alpha=0.10. Once completed, this trial will determine if the treatment is sufficiently promising to warrant further investigation in a multi-center, randomized trial.

11.2 Secondary objective: To estimate progression-free survival, patterns of failure and response rates in relation to values from historical control patients.

Progression Free Survival is defined as the time from study enrollment till the first of death from any cause or progression. Kaplan-Meier estimates of PFS will be generated for all patients on this trial and according to MGMT/IDH1 status. Additionally we will compare the observed PFS at 6 months and 1 year to published values from historical control patients.

Patterns of failure and response rates - Failures will be classified as central, in-field, marginal or distant, based on previously published criteria. Our hypothesis is that including high b-value diffusion and perfusion MRI in treatment planning will reduce the proportion of central failures within the high-dose radiation region. We will explore whether this appears to be the case by comparing this proportion to prior dose escalation studies based on conventional MRI planning alone.

Response rates - The proportion of complete, partial and any responders will be calculated along with 95% likelihood ratio confidence intervals using RANO criteria. The proportion of any responders will also be compared to published values from historical controls.

11.3 Secondary objective: Assess the ability of pre-therapy and week 3 MET PET scans and advanced MRI to determine sub-volumes at high risk of recurrence.

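### MGMT weighting is set out for overall survival but not extended to the historical comparisons of PFS and response in section 11.2

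*Combined protocol and SAP*

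**What the plan says.** Section 11.1 (primary objective) tests 12-month OS against a historical value: "We will test the null hypothesis that the true 12 months OS is equal to 0.65". It calls MGMT status prognostic, with a hazard ratio of about 2 for OS, and takes 30% methylated as the share in RTOG 0525 and RTOG 0825. It warns that with 40 patients "it is possible that the proportion of methylated patients will differ from 30% by a non-negligible amount". The remedy is to weight patients so that the "weighted proportion of methylated patients is equal to 30"%, using .3/p* for methylated and (1-.3)/(1-p*) for unmethylated patients, where p* is the observed methylated share.

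Section 11.2 (PFS, patterns of failure, response) also looks outward to historical controls. For PFS: "Additionally we will compare the observed PFS at 6 months and 1 year to published values from historical control patients". For response: "The proportion of any responders will also be compared to published values from historical controls". It mentions no weights for either. Kaplan-Meier PFS curves by MGMT/IDH1 status are planned but are not linked to the historical comparison, and response has no MGMT breakdown. No later section carries the weights to secondary endpoints. Section 8.3 has MGMT status documented as part of standard practice.

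**The concern.** The reason given for weighting in 11.1 is that a small single-arm cohort may by chance have a different MGMT mix from the published controls. That reason does not depend on the endpoint. It applies to any comparison with external controls if MGMT affects the outcome.

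A high methylated share would then make PFS look better than the controls with no treatment effect, and a low share would hide part of a real gain. OS would be standardized and PFS would not, so the two could point in different directions through case mix alone. Because 11.2 does not state the method, it could also be chosen after p* is known. Sections 2.0 and 11.0 say the results should show whether the regimen merits a randomized trial, and PFS and response will be read with that in mind.

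**Working it through.** **Plan's own figure first.** The power statement rests on this basis: "These results are based on an exact 1-sided test at alpha=0.10". With 10% non-evaluable, n = 36 and n = 72.
- n = 36: reject at 28 or more alive; alpha 0.0725, power 0.813 at 82%.
- n = 72: reject at 53 or more alive; alpha 0.0773, power 0.851 at 78%.

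Both exceed 80%, so the stated power reproduces. It concerns OS only and this point does not affect it.

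**Inputs from section 11.1.** Reference share 30%; MGMT hazard ratio about 2, for OS; historical 12-month OS 0.65.

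**Assumptions (not in the documents).** PFS hazard ratio 1.3 to 2, with unmethylated patients doing worse; control PFS 40-60% at 6 months and 20-30% at 1 year.

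**Step 1: how far the share can move.** The methylated count is Binomial(n, 0.3).

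| n | SD of share | central 95% range | P(10 points or more from 30%) |
|---|---|---|---|
| 40 | √(0.3×0.7/40) = 7.2 points | 17.5% to 45% | 0.226 |
| 80 | √(0.3×0.7/80) = 5.1 points | 20% to 40% | 0.066 |

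**Step 2: stratum rates.** For overall rate S and hazard ratio HR, solve 0.3·u^(1/HR) + 0.7·u = S for the unmethylated rate u; the methylated rate is m = u^(1/HR). With no treatment effect, the unweighted estimate is shifted by (p* − 0.30)(m − u). With weights to 30% the expected shift is 0.

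**Step 3: the shift the plan removes (OS).** S = 0.65, HR 2: u = 0.597, m = 0.773. At p* = 0.45 the shift is 0.15 × 0.1755 = +2.6 points.

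**Step 4: the shift left in PFS.**

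| Assumed control PFS | HR | u | m | shift at 45% | shift at 40% |
|---|---|---|---|---|---|
| 6 months, 60% | 1.3 | 0.577 | 0.655 | +1.2 | +0.8 |
| 6 months, 60% | 2 | 0.542 | 0.736 | +2.9 | +1.9 |
| 6 months, 50% | 1.3 | 0.473 | 0.562 | +1.3 | +0.9 |
| 6 months, 50% | 2 | 0.432 | 0.658 | +3.4 | +2.3 |
| 1 year, 30% | 1.3 | 0.271 | 0.367 | +1.4 | +1.0 |
| 1 year, 30% | 2 | 0.225 | 0.475 | +3.7 | +2.5 |

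Shifts are in percentage points. Assumed controls of 40% at 6 months and of 20% or 25% at 1 year give shifts inside the same 1.2 to 3.7 range at 45%. Shares below 30% give the same sizes with the opposite sign.

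**Step 5: against sampling error.** At n = 40, √(0.3×0.7/40) = 7.2 points and √(0.5×0.5/40) = 7.9 points. The largest shift is about half a standard error.

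**Response.** The documents give no MGMT effect on response, so no size is computed.

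**The case against.** Much of the case on the other side stands.

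- **That the weights are excluded is an inference.** It rests on the plan's reference to observed PFS and on silence about weights. Section 11.1 describes the weighting as part of the statistical analysis and defines it per patient, which could be read to cover all endpoints. But it sits under the primary objective and is justified only by an OS hazard ratio. On either reading, 11.2 needs a clarifying sentence.
- **PFS by MGMT/IDH1 status is planned.** The imbalance will be visible, and PFS could be standardized from that output. This does not commit the historical comparison to it and does not cover response.
- **The effect is uncertain and modest.** At a hazard ratio of 1.3 the shift at 45% is only 1.2 to 1.4 points. A share of 45% or more has probability 3.2% at n = 40 and 0.3% at n = 80, and joint analysis of 80 patients is expected.
- **The 30% target may not fit.** It is tied to RTOG 0525 and RTOG 0825, and 11.2 does not name its comparators. Weighting to 30% could worsen comparability with a control group of another mix.

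A reader might go further and infer an inflated false-positive rate for PFS. The documents do not support that. Section 11.2 sets no test, alpha or threshold; "The test will be one-sided at an alpha=0.10 level" belongs to the OS test. Any such rate would also hold only for a given observed share. If the expected share is 30%, the shift averages zero over chance.

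**Conclusion.** The point holds as an inconsistency between 11.1 and 11.2 that affects the accuracy of secondary estimates. Followed as written, 11.2 leaves in an MGMT imbalance that 11.1 judged worth removing for OS. If the PFS hazard ratio is near 2, the PFS shift is at least as large as the OS shift removed (2.9 to 3.7 points against 2.6, at 45% methylated). If it is near 1.3, the shift is about 1.2 to 1.4 points. At the upper end of the range for 80 patients (40%), it is about 0.8 to 2.5 points. The sizes rest on assumed PFS hazard ratios and control rates.

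The primary test, its power and the sample size are not touched, and no decision rule depends on these comparisons. For response only the inconsistency is shown, not a bias of known size.

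**What to change.** Add to section 11.2:

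- PFS at 6 months and 1 year will be compared with historical controls after MGMT standardization, as 0.3 × PFS(methylated) + 0.7 × PFS(unmethylated), from the Kaplan-Meier curves by MGMT status, with variance 0.09 × Var(methylated) + 0.49 × Var(unmethylated).
- The response proportion will be standardized in the same way as a supporting analysis.
- The 30% share applies when the comparator is RTOG 0525 or RTOG 0825. Otherwise the comparator will be named and its published methylated share used, with the coefficients changed to match.
- Unweighted values will be reported alongside.

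The cost is a short insertion and no new data. The effect on precision depends on the observed share. With an assumed 1-year PFS of 30% and HR 2 (0.475 methylated, 0.225 unmethylated) at n = 40:

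- 15% methylated (6 and 34 patients): weighted SE = √(0.09×0.475×0.525/6 + 0.49×0.225×0.775/34) = 0.079. The unweighted SE is 0.068 with stratum sizes fixed, or 0.070 as a simple binomial. The increase is 14% to 16%.
- 45% methylated (18 and 22 patients): weighted SE 0.072, unweighted 0.072 with stratum sizes fixed, so essentially unchanged.

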6.0 RADIATION THERAPY

6.1 Radiation Dose and Fractionation

Radiation therapy will be delivered once daily for a total of 30 fractions, five days per week. If treatment is interrupted due to a non dose-limiting adverse event or any reason other than toxicity, including holidays, weather, transportation, or treatment machine problems, the duration of treatment will be extended accordingly. An initial treatment plan will be designed to simultaneously deliver differing doses per fraction to 2 PTV volumes: 60 Gy to the conventional MRI volume (PTV_Low), which is the volume and dose used in standard practice. An additional simultaneous boost will be delivered to the combination of high b-value diffusion and perfusion abnormality alone (PTV_High, the area assumed to be at highest risk of tumor recurrence).

Patients with a negative postoperative high b-value DW-MRI and perfusion MRI following complete resection will be treated to the post-operative resection cavity and conventional T1 MRI contrast-enhancing region to a total dose of 60 Gy, as per standard of care, and will remain on study to be analyzed with the entire study cohort. A negative high b-value DW-MRI or perfusion MRI will be defined as a combined high b-value DW-MRI and perfusion target volume of 1 cc or less. Radiation dose will be prescribed to ensure that at least 95% of the PTV (D_{95%}) should be covered by 100% of the prescription dose.

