6.2 Target Volumes

Target volumes will be based on the postoperative conventional MRI, and high b-value diffusion as well as perfusion MRI. Pre-operative conventional MRI should be reviewed in correlation with the post-operative residual tumor bed as per standard of care. Target volumes for this treatment are as follows:

Gross tumor volume, conventional MRI (GTV Low): shall be defined as the area of enhancement plus surgical cavity on pre-radiotherapy T1-gadolinium enhanced MRI, as per standard practice. If the conventional MRI does not show any abnormal enhancement, the GTV_Low will include the surgical cavity alone, as per standard practice.

Gross tumor volume, high b-value DW-MRI and perfusion MRI (GTV^HCV perf): shall be defined as the area of abnormality on pre-radiotherapy high b-value diffusion MRI and perfusion MRI. The HCV target volume will be defined as previously published 18 on b=3000 s/mm² diffusion weighted imaging by a threshold technique (mean intensity plus 2 standard deviations) calculated from a volume of interest in the normal-appearing brain tissue in the contralateral brain from the tumor.

Clinical target volume, conventional MRI (CTV Low): GTV_Low will be expanded by 1.7 cm to account for microscopic disease extension, and edited out of normal structures (e.g. calvarium, falx) as per standard of care.

Clinical target volume, high b-value DW-MRI and perfusion MRI (CTV^HCV perf): CTV^HCV will be set equal to the GTV^HCV

Planning target volume, conventional MRI (PTV Low): CTV_Low will be expanded by a margin of 0.3 cm, to account for daily patient set-up variability

Planning target volume, high b-value DW-MRI and perfusion MRI(PTV_High): CTV^HCV_perf will be expanded by a margin of 0.3-0.6 cm, or as appropriate to account for registration and daily patient set-up variability.

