Several approaches are possible, ranging from very ad hoc qualitative analysis to complex voxel level image analysis. Here we describe an empiric approach to assessment of the ability of an image to predict volumes at highest risk of recurrence. The goal is to compare the probability of the imaging defined subvolume recurring with the probability of the rest of the tumor recurring. This comparison must take into account two potential confounding variables. First, these two (absolute) volumes will typically be different for a given patient and thus any analysis regarding location of recurrence must be weighted by volume. Second, the imaging defined volume may receive higher (or lower) dose than the rest of the tumor. One means to do this is to stratify the analysis on dose received. For example, assume we categorize the initial PTV in terms of high-dose and low-dose regions. Then for each region (strata) we could compute the following quantities

- 1) P1=Proportion of the imaging sub-volume overlapping with recurrence volume (rVOI)
- 2) P2=Proportion of the non-imaging sub-volume overlapping with rVOI

Evidence for success of the imaging at goal to 'determine tumor sub-volumes at high risk of recurrence' would be given when P1>P2. Across the population of patients, we could perform a stratified test whether E[P1] > E[P2]. Metrics such as sensitivity and specificity will be used to quantify the spatial predictive ability and will be calculated as proportions of volumes. For example, for sensitivity we will calculate the proportion of the rVOI contained in the imaging subvolume. Predictive values (PPV and NPV) could be calculated in a similar manner.

Summary statistics will also be generated describing the volumes of each of these imaging defined sub-volumes and their overlap.

11.4 Secondary objective: To prospectively compare tumor volumes defined by baseline MET PET with baseline high b-value DW-MRI and perfusion MRI A conformality index⁴² will be calculated that compares the MET-PET defined tumor volume with high b-value DW-MRI and perfusion MRI defined tumor volume. Non-overlapping regions of MET-PET tumor volume and MRI tumor volume as well as the overlapping regions will be calculated for each patient and used to calculate conformality indices. Assuming the endpoint is normally distributed, the 95% confidence interval for the mean has half-width = 1.96*Standard error of the mean.

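### For the combined baseline diffusion/perfusion volume in boosted patients, the dose-stratified P1-versus-P2 comparison in 11.3 does not exist in the low-dose stratum and reaches only the boost margin in the high-dose stratum

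*Combined protocol and SAP*

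**What the plan says.** Section 11.3 sets out to "compare the probability of the imaging defined subvolume recurring with the probability of the rest of the tumor recurring". It names two confounders, unequal volumes and unequal dose. For dose it describes one adjustment, introduced as an example: "For example, assume we categorize the initial PTV in terms of high-dose and low-dose regions". Within each region P1 is the share of the imaging sub-volume overlapped by the recurrence, and P2 is the same share for the non-imaging part. Evidence of success "would be given when P1>P2", with a stratified test of the two means across patients as an option. It adds: "Metrics such as sensitivity and specificity will be used to quantify the spatial predictive ability". No dose cut-off is given. Pre-therapy and mid-treatment MET PET and advanced MRI are in scope. (11.3 says week 3 for the mid-treatment scan and the calendar in 10.2 says week 4; the calendar's label is used here.)

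The radiation sections define the boost from the same images. Under 6.1 it is "delivered to the combination of high b-value diffusion and perfusion abnormality alone". Under 6.2, "CTV^HCV will be set equal to the GTV^HCV", and the CTV is then "expanded by a margin of 0.3-0.6 cm, or as appropriate to account for registration and daily patient set-up variability" to give PTV_High. Section 6.3 prescribes 75 Gy to PTV_High with a 95% minimum and 60 Gy to PTV_Low. It also allows documented compromises of the target to spare the visual pathway or brainstem. Patients with a combined volume of 1 cc or less are treated to 60 Gy without a boost.

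**The concern.** Stratifying on dose removes dose confounding only if each stratum contains both kinds of tissue. Here the image being judged also decides who gets the high dose, so for the combined baseline volume imaging status fixes the dose stratum. The planned enrollment of 40 consists of boost-eligible patients (sample size paragraph of 11.1), so this affects the main cohort.

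At stake is how a named secondary objective is read. P1>P2 could be reported as success for the trial's principal imaging volume when the comparison is only with a few millimeters of surrounding margin. A reader could not separate the value of the image from the location of recurrences.

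A smaller, related point concerns 11.2. The share of central failures is scored on this trial's diffusion/perfusion high-dose region and compared with earlier dose-escalation studies planned on conventional MRI. In the center's own earlier study (1.0 Introduction) the target was the whole enhancing lesion. The share can therefore move because the reference region changed.

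**Working it through.** The plan states no figure for 11.3, so there is none to reproduce.

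**Step 1: which stratum holds the volume.** Inputs are from 6.1 to 6.3. The imaging volume equals the boost GTV, which equals the boost CTV and lies inside PTV_High. Minimum PTV_High dose = 0.95 x 75 = 71.25 Gy.

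- Cut-off clearly above 60 Gy and up to 71.25 Gy: all of the volume is high-dose. In the low-dose stratum P1 = 0/0, so there is no contrast.
- Cut-off at 60 Gy itself: 6.1 requires that at least 95% of the PTV "should be covered by 100% of the prescription dose", so nearly all of PTV_Low also counts as high-dose and dose is not controlled.

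This holds whether the combination means union or intersection of the two abnormalities.

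**Step 2: what P2 covers in the high-dose stratum.** It covers PTV_High minus the imaging volume, plus any fall-off tissue above the cut-off. The documents give no volumes, so these are assumptions: concentric spheres, no editing, no fall-off, a 20 cc sub-volume and GTV_Low of 40 cc.

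- Radius r = (3V/4π)^(1/3): 1.68 cm for 20 cc.
- Margin volume = (4/3)π(r + m)³ − 20: 12.7 cc at m = 0.3 cm, 29.9 cc at m = 0.6 cm.
- PTV_Low = 40 cc expanded by 1.7 + 0.3 = 2.0 cm: 293 cc.
- Share of the rest of PTV_Low: 12.7/273 to 29.9/273, about 4.6% to 10.9% (3.7% to 15.8% for GTV_Low from 60 down to 20 cc).
- Share of the rest of GTV_Low: 12.7/20 = 64% at 0.3 cm and 100% at 0.6 cm, where the margin extends past the 40 cc sphere. For a 60 cc GTV_Low: 12.7/40 = 32% to 29.9/40 = 75%.

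**Step 3: what drives P1>P2.** Assumptions: 20 cc sub-volume, 15 cc spherical recurrence, 0.45 cm margin. Recurrence centers scatter normally around a point at the stated distance from the boost center. P1 and P2 are mean overlaps divided by 20 cc and by the 20.7 cc margin. The image carries no information in this model beyond its position.

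| Distance of recurrence center | P1/P2, SD 0.5 cm | P1/P2, SD 1.5 cm |
|---|---|---|
| 0 cm | 0.546/0.145 | 0.155/0.107 |
| 1.5 cm | 0.266/0.166 | 0.112/0.085 |
| 2 cm | 0.151/0.135 | 0.086/0.070 |
| 2.5 cm | 0.067/0.092 | 0.062/0.055 |
| 3 cm | 0.021/0.048 | 0.041/0.040 |

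With centers uniform in a ball of radius 2.1 cm, P1/P2 is 0.288/0.170; at radius 4.1 cm it is 0.052/0.052. Margins of 0.3 or 0.6 cm give the same pattern. With sub-volumes of 5 to 40 cc and recurrences of 5 to 30 cc (SD 0.5 cm), mean P1 exceeded P2 in all 12 centered pairs and fell below it in 11 of 12 at 2.5 cm.

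**The case against.** **The method is only an example.** 11.3 says several approaches are possible and uses conditional wording. That is true, and the text does name dose as a confounder. But no other dose adjustment is described, and the success criterion attaches to this one. Sensitivity and specificity remain computable but are not dose-adjusted.

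**The contrast can still be computed.** This stands for the high-dose stratum, where the margin is not empty. A reader might infer that nothing can be estimated for this volume; the documents do not support that. The comparison is missing in one stratum and answers a different question in the other.

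**The margin may cover most of the remaining gross tumor.** Under the same assumed geometry it does for a 40 cc GTV_Low (64% to 100%). The 4.6% to 10.9% share is of PTV_Low, which includes a 2.0 cm expansion, so it does not show that the gross tumor is missed. The concentric layout is also only a convenience: the Introduction reports that 40% of each of the diffusion and perfusion volumes lay outside enhancement.

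**Dose may work against P1>P2.** The Introduction reports fewer central recurrences at higher dose, so the boost may lower P1 and the dose effect may be conservative. This stands, but confounding by location remains. A reader might infer a bias in favor of the image; none is shown, because the sign changes with assumed location and scatter.

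**The premise is not uniform.** Section 6.3 describes the boost volume by high b-value diffusion alone, whereas 6.1 and 6.2 use diffusion and perfusion. On a diffusion-only reading, perfusion-only tissue could fall in the low-dose stratum. These sections must be reconciled.

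**Conclusion.** The point holds for the combined baseline diffusion/perfusion volume, in boosted patients whose plan meets coverage. With a cut-off clearly above 60 Gy and up to 71.25 Gy, the low-dose contrast is not estimable. The high-dose contrast is estimable only against the PTV margin plus fall-off. P1>P2 there follows recurrence location (0.55/0.15 centered, 0.07/0.09 at 2.5 cm, SD 0.5 cm), so it is not evidence that the image identifies high-risk sub-volumes.

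The stratum result follows from the target definitions in 6.1 and 6.2 and the doses in 6.3. The P1/P2 sizes rest wholly on assumed spheres and scatter; the reversal at 2.5 cm disappears at SD 1.5 cm. Exceptions are documented coverage compromises and unboosted patients.

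It would be too strong to say that 11.3 as a whole fails: MET PET and week-4 volumes do not define the boost. The primary survival test is untouched. The 11.2 point is minor, in an analysis worded as exploratory. Its size cannot be computed, because the definition of a central failure is not printed.

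**What to change.** In 11.3:

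1. State that, for the combined baseline diffusion/perfusion volume in boosted patients, the low-dose contrast does not exist and the high-dose contrast is against the margin only.
2. Report P1, P2, sensitivity and specificity for this volume descriptively, labelled as confounded by location and dose. Note that the boost may lower P1.
3. Do not apply the P1>P2 success criterion to it.
4. Use the stratified test for volumes that do not define the boost (MET PET, week-4 MRI), only in strata that contain both imaging and non-imaging tissue. State two limits: MET PET is optional and small (first 30 patients at baseline, up to 10 at week 4), and any volume nested in the boost shares the geometric problem.
5. Reconcile the description of the boost volume in 6.3 with 6.1 and 6.2.

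Items 1 to 4 need SAP wording only. The downside is that the conclusion for the trial's main imaging volume becomes descriptive.

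Optional, in 11.2: keep the planned scoring and add a sensitivity scoring of the same failures against a conventional-MRI reference. Do not attribute a lower central share to the new planning unless both agree. Because GTV_Low includes the surgical cavity, matching the earlier target may need an enhancement-only contour. The cost is one extra scoring, and possibly one contour, per failing patient, with no new scans.

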Conventional contrast-enhanced T1-weighted and T2-weighted magnetic resonance imaging (MRI) used for radiation planning reflects only anatomic rather than molecular or biologic properties of the tumor. In contrast, advanced imaging with amino acid PET using carbon-11 (¹¹C) labeled methionine (MET PET) and advanced MR imaging may improve our ability to better define tumor extent and delineate the regions at highest risk for failure in high-grade gliomas.⁹

FDG-PET has demonstrated relatively less sensitivity in smaller tumors, intrinsic uptake within normal gray matter and reduced uptake in radiotherapy treated areas compared

to MRI.¹⁰ In contrast, promising results have been obtained with L-methyl-¹¹C-methionine.¹¹C-methionine is an amino acid tracer with increased uptake in high grade gliomas related to increased activation of carrier-mediated transport at the blood-brain barrier and subsequent elevated protein synthesis.¹¹⁻¹² Animal studies have shown that reduction in ¹¹C methionine uptake after radiation precedes the development of tumor necrosis and tumor shrinkage, and the extent of the response seems to correlate with outcome.¹³ Clinical evidence now suggests that MET PET identifies glioma beyond the region identified by conventional MRI.¹⁴⁻¹⁵ A phase II trial in recurrent gliomas showed improved outcome when comparing conventional MRI to biologic target volume definition using MET PET.¹⁶

We have assessed the ability of MET PET to define tumor volume in a dose escalation study of GBM in which the targets were defined based on standard MRI. Pre-radiation MET PET was obtained in all patients. The majority of patients' MET PET showed uptake beyond the contrast-enhanced MRI. The found that in addition to better demonstration of the extent of tumor compared to standard MRI, MET PET prior to treatment is a better modality to identify sites of future tumor recurrence. Twenty-six patients were evaluated and 19 had appreciable (>1cc) volumes of increased MET PET activity pre-therapy. In 5 patients the tumor target based on conventional MRI did not fully encompass the MET PET-defined tumor and all 5 patients had non-central failures contiguous with the MET PET defined tumor, compared with 2/14 patients whose MET PET-defined tumors were encompassed by the high-dose targets and had non-central failures. Thus, inadequate MET PET coverage was associated with increased risk of non-central failures (p<0.01).

Functional MR Imaging

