- and at the time of advanced imaging follow-up (3 months post-RT and/or at the time of suspected progression).
- c) QOL/MDASI/MMSE evaluations will be undertaken at baseline, , 6 weeks (end RT), 1 month, 7 month, 13 month, 19 month (+/- 6 weeks) after the end of chemoradiation, typically at the time of standard clinical follow-up and preferably close to the date of imaging if imaging is obtained. Neurocognitive evaluation will be undertaken at baseline, 1 month, 7 months, and 19 months after chemoradiation (+/- 6 weeks).
- d) CBCD to be drawn weekly during radiation, and prior to every cycle of adjuvant chemotherapy, beginning with first cycle as per standard of care. Comprehensive metabolic panel will be drawn at least every 8 weeks, or more frequently at primary oncologist's discretion, as per standard practice.
- e) Clinical gadolinium enhanced MRI brain scans will be obtained as per standard clinical practice approximately every 8 weeks after chemoradiation, or per the treating physician's discretion as per standard practice.
- f) Up to 10 patients will optionally receive MET PET during Wk 4. All patients will receive advanced MRI (see appendix for details) at Wk 4 (between fractions 17-20), and an additional advanced MRI scan will be obtained 3 months (+/- 1 week) after completion of chemoradiation and/or at the time of suspected tumor recurrence.
- g) Patients will be followed for tumor progression and survival for up to 5 years from the end of radiotherapy. Tumor progression and date and cause of death will be documented, if known. Studies available in the clinical setting may also be used for study purpose as indicated under study aims.
- i) Only the first 30 patients total will optionally receive pre-radiotherapy MET PET

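### Section 11.4 uses 1.96 standard errors for a 95% interval on at most 30 patients, so the interval is slightly too narrow

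*Combined protocol and SAP*

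**What the plan says.** Section 11.4 covers the comparison of baseline tumor volumes between MET PET and advanced MRI: "A conformality index⁴² will be calculated that compares the MET-PET defined tumor volume with high b-value DW-MRI and perfusion MRI defined tumor volume". Each patient with both scans contributes one index. The section then says: "Assuming the endpoint is normally distributed", "the 95% confidence interval for the mean has half-width = 1.96*Standard error of the mean". It gives no standard deviation, no expected n and no numerical half-width.

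The number of patients who can contribute is set elsewhere. Footnote i to the calendar in Section 10.2 reads: "Only the first 30 patients total will optionally receive pre-radiotherapy MET PET". The schema and the calendar also mark the scan as optional.

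**The concern.** The value 1.96 is the normal quantile. It gives a true 95% interval for a mean when the standard deviation is known, and nearly so when n is large. Neither condition is met here: the standard deviation has to come from the same patients, there are at most 30 of them under this protocol, and there will be fewer if some decline. An interval built this way falls short of its stated coverage.

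At stake is an error bar labelled 95% that is not quite that. It is the only interval specified for this objective, so an analyst following Section 11.4 to the letter would report it.

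**Working it through.** **Inputs**

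- Multiplier 1.96, 95% two-sided, index assumed normal: Section 11.4.
- Standard deviation: none given, so the standard error is estimated from the sample.
- Maximum n with a baseline MET PET: 30 (Section 10.2, footnote i).
- Possible pooling: Section 11.1 plans 40 patients at this center and 40 at a second, and says "we expect to jointly analyze the data from all 80 patients following trial completion". The documents do not say whether the limit of 30 covers both centers. If it applied to each, n could reach 2 × 30 = 60.
- Values of n below 30: assumptions, since no uptake rate is given. One has an anchor in the Introduction, which reports for an earlier study: "Twenty-six patients were evaluated and 19 had appreciable (>1cc) volumes of increased MET PET activity pre-therapy". If only that share of 30 scans gave a usable volume, n = 30 × 19/26 = 21.9, about 22.

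**Step 1. Reproduce the plan's figure.** The 97.5th percentile of the standard normal is 1.95996, which rounds to 1.96. The plan's multiplier is therefore the known-SD or large-sample value. There is no numerical half-width to check beyond that.

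**Step 2. Exact multiplier.** For normal data with an estimated standard error, (mean − true mean)/SE follows a t distribution with n−1 degrees of freedom, so the exact 95% multiplier is t(0.975, n−1).

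**Step 3. Actual properties of the 1.96 interval.**

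- Coverage = 1 − 2·P(T with n−1 df > 1.96)
- Shortfall in width = 1 − 1.96/t(0.975, n−1)

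At n = 30: t(0.975, 29) = 2.045; shortfall = 1 − 1.96/2.045 = 4.2%; coverage = 94.0%.

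| n | Basis | t(0.975, n−1) | Too narrow by | Actual coverage |
|---|---|---|---|---|
| 60 | limit applied per center, data pooled | 2.001 | 2.0% | 94.5% |
| 30 | limit in footnote i | 2.045 | 4.2% | 94.0% |
| 25 | assumed | 2.064 | 5.0% | 93.8% |
| 22 | 19/26 of 30, assumed | 2.080 | 5.8% | 93.7% |
| 20 | assumed | 2.093 | 6.4% | 93.5% |
| 15 | assumed | 2.145 | 8.6% | 93.0% |
| 10 | assumed | 2.262 | 13.4% | 91.8% |

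**Step 4. Check by simulation.** With 400,000 normal samples at each of n = 30, 22 and 10, the 1.96 interval covered the true mean in 94.0%, 93.7% and 91.8% of samples. The t interval covered it in 95.0% each time.

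**The case against.** The best defense is that nothing has been miscalculated. Section 11.4 states the familiar large-sample form in one line, perhaps to convey precision rather than to instruct the analyst, and a t interval could still be used at analysis. At the one n the protocol supports, the loss is one percentage point of coverage. The larger figures need a low uptake that the documents do not predict; the limit of 10 in footnote f concerns the week 4 scan, not the baseline scan used here. Pooling with the second center might raise n to 60. The t interval is itself exact only under normality, and the index is defined through a cited source not available here, so departure from normality could matter more than the multiplier. Finally, no test, threshold or decision depends on this interval.

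Much of this stands, and it is why the point is minor. The effect to quote is the one at n = 30, and smaller n must be labelled as assumptions. Three parts do not rescue the sentence. As a precision statement it conveys nothing, because it has neither an n nor a standard deviation, and no other interval is named. Pooling to 60 shrinks the shortfall but does not remove it. And normality is the plan's own assumption: under it, t is the exact multiplier and 1.96 is not.

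**Conclusion.** The concern holds. As written, the interval in Section 11.4 is too narrow for its 95% label: by 4.2% in width, with 94.0% coverage, at the maximum of 30 patients. The range runs from 2.0% and 94.5% if 60 scans were pooled to 13.4% and 91.8% if only 10 patients took up the scan. These figures rest on the plan's assumption of a normal index, on a standard deviation estimated from the data, and, away from n = 30, on assumed uptake or pooling.

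This is a correction of low priority. The objective is secondary and descriptive, and the 12-month survival test, the sample size and the toxicity stopping rule do not depend on it.

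**What to change.** In Section 11.4, replace 1.96 with the 97.5th percentile of the t distribution with n−1 degrees of freedom, and define n as the number of patients with both a baseline MET PET and baseline advanced MRI. Add that n is at most 30 under footnote i, and say whether that limit covers this center alone or both. If the observed indices are clearly not normal, a bootstrap interval could be named as the alternative.

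The cost is a line of text. No patients, scans or procedures are added, the t multiplier adapts to whatever n is reached, and the reported interval becomes about 4.3% wider at n = 30 (2.045/1.96 = 1.043).
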